#### Community-Engaged Research Framework

Trust and mistrust play an important role in the Muslim community's social interactions, which face discrimination in the U.S. every day. This research will only be able to recruit participants if community leaders understand and actively promote it. The Mosques are the centers of social interaction in Muslim communities. This project needs to engage the Imams at Mosques in and around Richmond, VA.

The community-engaged framework will implement a Community Action Model (CAM). The CAM is a five-step process that starts with recruiting and building relationships with community partners and developing and implementing a sustainability plan. The CAM is fit for the community engagement part of our project due to the capability to involve the community members in every aspect of the design, implementation, and evaluation of these community action plans. The CAM was selected to inform the CBPR approach due to the main aspects of the model that help 1) The community members to understand and command the policies, systems, and environment that affect their lives intending to advance health equity, and 2) Build the capacity of communities to create sustainable changes to improve the cancer-related health and well-being of their communities. Our project has a 12-month planning period that focuses on building community capacity, developing community partnerships, and establishing community volunteers' networks, whose purpose will be to design community-driven strategies to eliminate cervical cancer disparities in the Muslim community in the Richmond area.

The first step of the CAM is recruiting and training community leaders inside Mosques, building the relationships between the research team and Imams of Mosques, and providing all information they need to understand cervical cancer, screening for it, and HPV vaccination. The second step is community diagnosis; the research team will support community leaders in developing the research plan to outline their research questions and methodology to understand cervical cancer's local implications. The third step is the analysis and presenting findings; the research team must deliver their results back to community members. The fourth step is an action plan; the research team develops and implements a pilot or demonstration project that shows the chosen action/activity's feasibility and effectiveness. The fifth step is to build the capacity to maintain and enforce the action project teams by developing and implementing a sustainability plan.

#### Community-Engaged Infrastructure

The study will be based in Virginia, home to a diverse population of over 250,000 Muslims, most living in Northern and

Central Virginia. The population density correlates with the availability of Mosques, ethnic food stores and restaurants, and Muslim schools. The project will work toward building a strong community partnership between the Virginia Commonwealth University and the Islamic Center of Virginia (ICR) by establishing Community Advisory Boards (CABs) and engaging Community Peer Researchers (Figure 2).

CABs commonly formalize the academic–community partnerships that guide CBPR by providing a mechanism for community members to influence research activities. The CABs will include religious leaders from the ICR, which is suggested by previous studies. We will target scholars with expertise in behavioral interventions, Islamic theology, and law, as well as community-based participatory research to include in the committee. The two main sects of Islam are Sunni and Shia, therefore we decided to recruit both Sunni and Shia representatives to reach as many Muslim American women as possible. There are no female religious leaders in Mosques, so we can only have male religious leaders as members of the CABs. Using religious voices to communicate about our project will enhance participation in the study. Getting permission from Mosque leaders to be at the Mosque in person during worship day (Friday) will greatly help with the study progress.

Community Partnerships: For this study, the Massey Cancer Center (MCC), Virginia Commonwealth University, will be partnering with the community. MCC is located in Richmond, VA, in our target geographic area. MCC is well-known for the quality of the service that is provided for its patients, and it also has a diverse set of researchers and research staff who are well-versed in community-involved research. One of the MCC goals is to reduce cancer disparities by improving healthcare services and cancer outcomes among minorities in the Richmond area, which fits well with the goals of our project. The partnership with MCC will significantly enhance our research project as it will provide recognition and trust. It will also secure better relationships with the community.

Since we will not have the opportunity of having Muslim women in the CABs, we decided to engage female peer researchers to cover cultural sensitivities and reach a high number of Muslim women. Peer researchers will serve as partners with full involvement and authority in research processes. The eligibility criteria will be adult women who identified themselves as Muslims. Age plays an important role in Muslim culture; participants will be more trusting to what more grown community members provide more than the new generation. Peer researchers should have advanced English skills (speak, write, and read) and use technology to easily overcome the language barriers and communicate with the research team. Our preference is to recruit women and peer researchers who have been visiting the Mosque for at least 5 years to have enough experience with interacting with Mosque visitors and Islamic and Mosque rules and etiquette. We will also pursue building a strong relationship with Muslim women who are coming to take classes inside the Mosque. Peer researchers will develop a better connection with the research participants due to their shared life experiences as women having the same religion and traditions and familiarity with social norms. The peer researchers will have to be trained in research processes. Our expectation is that the targeted peer researcher cohort will not have difficulties with training, but they might have challenges regarding the schedule and availability. Most Islamic centers open on Fridays, and the is hours when which people practice their worship are usually between 12–1 PM, during regular business hours in the U.S. To overcome this problem, we will have 2 peer researchers, and each woman will cover a day per month.

**2. \* Describe the study hypothesis and/or research questions. Use lay language whenever possible.**

Aim 1b. We will conduct individual interviews with key stakeholders in our Community Advisory Board (Muslim religious leaders (N=4)) to receive feedback on the developed materials and inform the intervention program. This aim includes the Phase II (Preliminary Testing) of the ORBIT model (proof of concept, prepare the pilot).  
 Aim 2. We will test the preliminary efficacy of the religiously tailored and culturally appropriate intervention program. H1. Participants will show significant improvements in knowledge and acceptance of cervical cancer prevention after the intervention. To test this hypothesis, we will conduct a pre-post survey to examine changes in knowledge and acceptance of cervical cancer screening and prevention. This aim includes the Phase II (Efficacy) of the ORBIT model.  
 Aim 3. We will test the feasibility and acceptability of the religiously tailored and culturally appropriate intervention program which includes education and experiential practice/communication skills training. We will recruit 20 participants with the same eligibility criteria as in Aim 1, who have not participated in our previous studies, and conduct a single-arm pilot trial. H2. We hypothesize that the religiously tailored and culturally appropriate intervention program will be feasible to conduct as evidenced by meeting enrollment targets and the ability to implement the program as planned. H3. The intervention will be acceptable as evidenced by engagement (>60%) and retention (>80%), and satisfaction survey ratings.

**3. \* Describe the study's specific aims or goals. Use lay language whenever possible.**

Our team also investigates the barriers faced by MAW in the US healthcare system by evaluating the cultural competency of healthcare providers related to the Muslim culture at the VCU health system. Our ongoing work with the Muslim community has informed us about the community's needs. In this project, we will implement an interventional program guided by a community-based participatory approach utilizing expert-led education sessions and peer-led interventions, which combine health-related religious teachings and scientific information about the benefits of CC-S and HPV-Vax. The Muslim Community Partners (MCPs) will collaborate with our institute (VCU) by reaching out to four Islamic religious centers in Virginia. Partnership with Islamic centers is valuable to our project due to their ability to convince women to join our study, reach out to a high number of MAW, and because religious voices will be a good motivator for Muslim families to change. The primary outcome is increasing awareness of cervical cancer prevention methods. The secondary outcome is the acceptability and confidence/trust in cervical cancer prevention methods such as CC-S and HPV Vax.

The research questions are: Would MAW intend to do cervical cancer screening and uptake the HPV Vaccination after an education program supported by the Mosques that they frequently visit?

The aims of the study are:

Aim 1b. We will conduct individual interviews with key stakeholders in our Community Advisory Board (Muslim religious leaders (N=4)) to receive feedback on the developed materials and inform the intervention program. This aim includes the Phase II (Preliminary Testing) of the ORBIT model (proof of concept, prepare the pilot).

Aim 2. We will test the preliminary efficacy of the religiously tailored and culturally appropriate intervention program. H1. Participants will show significant improvements in knowledge and acceptance of cervical cancer prevention after the intervention. To test this hypothesis, we will conduct a pre-post survey to examine changes in knowledge and acceptance of cervical cancer screening and prevention. This aim includes the Phase III (Efficacy) of the ORBITT model.

Aim 3. We will test the feasibility and acceptability of the religiously tailored and culturally appropriate intervention program which includes education and experiential practice/communication skills training. We will recruit 20 participants with the same eligibility criteria as in Aim 1, who have not participated in our previous studies, and conduct a single-arm pilot trial. H2. We hypothesize that the religiously tailored and culturally appropriate intervention program will be feasible to conduct as evidenced by meeting enrollment targets and the ability to implement the program as planned. H3. The intervention will be acceptable as evidenced by engagement (>60%) and retention (>80%), and satisfaction survey ratings.

For these aims, we will use a survey that includes:

Pre-test survey, the scales are:

1. Demographic
2. Perceived Discrimination
3. Religious Discrimination
4. Spiritual Health Locus of Control.
5. Modesty
6. Cervical Cancer Knowledge
7. Perceived risk
8. Cuse of action
9. Self-efficacy
10. Attitude about CC screening
11. HPV vaccination acceptability

Post-test survey, the scales are:

2. Perceived Discrimination
3. Religious Discrimination
4. Spiritual Health Locus of Control.
5. Modesty
6. Cervical Cancer Knowledge
7. Perceived risk
8. Cuse of action
9. Attitude about CC screening
10. HPV vaccination acceptability
11. General Self-Efficacy Scale (GSES)
12. Cervical Cancer Screening Self-Efficacy Scale

Satisfactory survey are:

- Experience with the intervention.
- Acceptability of content
- Acceptability of delivery

**4. \* Describe the scientific benefit or importance of the knowledge to be gained:**

The Muslim population represents a significant, and increasingly growing, portion of the US population. Although literature shows the general lack of knowledge of Muslim women that are related to cervical cancer, there is a lack of educational intervention programs targeted toward Muslim women. Our study will implement the first educational program for Muslim women in the US, thus the effectiveness of educational programs in conservative communities could be assessed.

**5. \* Describe any potential for direct benefits to participants in this study:**

The study will provide valuable information for the Muslim community or the general population. increase knowledge will increase the seeking for care: cervical cancer screening. Decreasing vaccine hesitancy

1. By the end of year one, 5% of the conservative Muslim Women in Richmond, Virginia will know that the HPV vaccine is safe and effective.
2. By the end of year one, 5% of conservative Muslim women in the Richmond Virginia Area will know that the HPV vaccination will not cause their children to become sexually active before marriage.
3. By the end of year two 8% of conservative parents of Muslim girls in the Richmond Virginia Area will know that the HPV vaccination does not impact fertility and will permit administration of the vaccine to their daughters and sons
4. By the end of the program most women will seek for Cervical cancer screening: pap smear test

**6. \* Describe any potential for direct social impact in this study . For example, any engagement with specific communities to respond to community-identified needs, or ways the study will strengthen the well-being of the specific communities if applicable:**

Evidence shows that cervical cancer prevention methods such as screening and getting HPV vaccine are essential to decrease the mortality rate due to cervical cancer, however, these valuable tools are not used in adequate rates by the Muslim community. Therefore, understanding the Muslim women's behaviors and offering an educational program to provide individuals with crucial insight into these tools.

**7. Upload a supporting citation list if applicable:**

Document Name	Document	Version	Date Modified By	Uploaded Type	Approved
View Consent form - focus group	[name]- Consent 0.03 from of focus group	7/8/2023 1:09 AM	[name]	Consent/Assent/Information Sheet	Yes
View Consent form - Intervention program	[name]- Consent 0.04 from of Intervention group	7/8/2023 1:09 AM	[name]	Consent/Assent/Information Sheet	Yes
View Fund Plan	[name] -Budget 04.13.2023.xlsx	5/12/2023 11:52 AM	[name]	Funding Proposal	Not Applicable
View Education session	[name] Education session guide , intervention group- 04.07.2023.docx	5/12/2023 10:52 AM	[name]	Other	Yes

Document Name	Document	Document	Version	Date Modified By	Uploaded Type	Approved
View Timeline Plan	[name], timeline for PROMIS women Project-.docx	0.02	5/12/2023 10:43 AM	[name]	Other	Yes
View Conceptual model	[name] Conceptual Model 05.12.2023.docx	0.02	5/12/2023 10:40 AM	[name]	Research Measure	Yes
View Flyer 2	[name] Flyer Version 05.12.2023.docx	0.01	5/12/2023 10:39 AM	[name]	Other	Yes
View [name]-Focus group script guide	[name] -Focus Group Script Guide.docx	0.02	5/12/2023 10:24 AM	[name]	Other	Yes
View Participants -RA communication script	Participants -RA communication script .docx	0.01	5/12/2023 6:45 AM	[name]	Other	Yes
View Study Survey( Pre-post and satisfactory scales)	Survey- Promise women project 05.12.2023.docx	0.01	5/12/2023 6:35 AM	[name]	Research Measure	Yes
View consent form- focus group	Consent from - Focus group 02.20.2023.docx	0.01	2/20/2023 4:32 PM	[name]	Consent/Assent/Information No Sheet	
View VS biosketch	[name] Biosketch for AN 11.14.2022.pdf	0.01	2/20/2023 4:00 PM	[name]	CV/Biosketch	Not Applicable
View Communication log	Communication log.docx	0.01	2/20/2023 3:59 PM	[name]	Other	Yes
View PRMC approval	2022-10-10_MCC-22-19873_PRMC Approval Letter.pdf	0.01	10/10/2022 12:30 PM	[name]	Ancillary Committee Approval	Not Applicable
View Flyer	Flyer 004.08.2022.png	0.01	4/8/2022 6:09 PM	[name]	Other	Yes
View [name] Resume	[name]	0.01	4/3/2022 3:47 PM	[name]	CV/Biosketch	Not Applicable

Document Name	Document	Version	Date Modified By	Uploaded	Type	Approved
	06.07.2021.pdf			06.07.2021	pdf	

## Study Population

**1. \* Provide the maximum number of individuals that**

**1. May participate in any study interaction or intervention (including screening, consenting, and study activities)**

AND/OR

**2. You obtain any data/specimens about (regardless of identifiability)**

at VCU and at other sites under the VCU IRB's oversight. See the help text for additional guidance.

**2. If this is a multi-Center Project, what is the maximum anticipated number of subjects across all sites?**

**3. Provide justification for the sample size by explaining how you arrived at the expected number of participants and why this number is adequate for answering the research questions:**

Sample: A non-probability sampling (convenience sampling) method will be adopted to allow reach all potential participants. The team members will approach potential respondents at Islamic centers to participate in this study. The inclusion criteria include women aged  $\geq 18$  years who speak English, self-identify as Muslim, and have not participated in our pilot study before. The exclusion criteria are any participants who participated in our pilot study or are unable to provide valid consent (e.g., developmental disability).

Qualitative analysis side: to develop the education material we will recruit 10 female participants above 18 years old who identify as Muslim to participate in the design of the religiously tailored and culturally appropriate education materials for the intervention. First the focus group will help select the targets of the proposed education and the content to achieve each target (design). As a next step the focus group will focus on the formatting of the material, including basic usability testing (refine). Based on information from these sessions we will finalize the educational material for our intervention.

we will use the grounded theory for complete the analysis

Statistical Analysis for quantitative side : We assume that our study's CC-S HPV-Vax uptake rate would increase by 10% post-intervention. Based on a power analysis assuming the use of the student T-test to assess the difference in outcome between the intervention and control groups. The target sample size is estimated based on the G power software sample size calculator for the minimal sample size needed for an unlimited population size using a confidence interval of 80%, a standard deviation of 0.5, and a margin of error of 5%. The study requires 10 participants for intervention to test the feasibility of the program.

Descriptive summaries will be generated to summarize participant demographics and all study variables including individual and community characteristics, with a particular focus on religious adherence, modesty, knowledge, attitudes, and risk perceptions of CC-S and attitudes and intention to get the HPV-Vax. Means, standard deviations, and percentiles will be reported for continuous variables, frequencies, and percentages for categorical variables. Summaries will be stratified by gender, age, education, language, and community to explore patterns. Confidence intervals will be reported to convey the precision of all point estimates. Following the descriptive analyses, comparisons

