The intervention group will consist of 20 participants who will receive one education session divided into three sections/videos. The session will be offered in a single day and last 1.5 hours. The session will include the following topics: 1) Risk of HPV infection (30 minutes), 2) Cervical cancer risk (30 minutes), and 3) Advantages and benefits of early screening and the HPV vaccine (30 minutes).

All participants from both groups will be given the survey at month 0 (baseline) after the delivery of the educational material. The survey will be self-report, available in both hard copy and electronic form with a QR code for Redcap.

Participants are expected to take approximately 45 minutes to complete the survey.

The Islamic center offer private room to practice the research activities in both phases ( Focus group and single arm trial)

**5. \* Does this study have a separate protocol document (i.e. a multisite or sponsor's protocol) that contains a detailed description of the study's methodology?**

Yes

No

**6. \* Since a separate protocol document is not uploaded, describe the proposed research using language understandable to those IRB committee members whose expertise is not scientific. The description must include:**

- 1. A statement explaining the study design**
- 2. A detailed description of all the procedures that will be followed to carry out the study, preferably in sequential order, and in sufficient detail that the study's methods could be replicated**
- 3. The schedule and frequency of when and how procedures will be conducted (e.g. in person, online, phone, paper, etc.)**
- 4. A description of all research measures/tests/interventions that will be used, including analyses/tests conducted on specimens/biological samples (if applicable)**

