**See the help text for additional guidance**

**1. A statement explaining the study design**

**Study Design:**

The proposed study consists of two parts.

Part 1 involves formative research through a focus group to gather insights and reach saturation.

Part 2 is a single-arm pre and post-test trial with the objective of evaluating the efficacy of an educational interventional program.

The study aims to increase cervical cancer screening (CC-S) and HPV vaccine (HPV-Vax) rates among Muslim American women (MAW) in Virginia, leading to a reduction in cervical cancer (CC) incidence and mortality.

2. A detailed description of all the procedures that will be followed to carry out the study, preferably in sequential order, and in sufficient detail that the study's methods could be replicated.
  - a. Part 1 - Formative Research: Conduct a focus group with 10 participants until saturation is reached.
  - b. Part 2 - Single-arm Pre and Post-test Trial: Enroll 20 participants to evaluate the educational program's effectiveness.

Participants will complete a baseline survey to assess their knowledge, attitudes, CC-S and HPV-Vax practices, and predisposing factors.

The survey will cover topics such as CC knowledge, experiences of medical mistrust, discrimination, spiritual coping, and fatalism.

3. The schedule and frequency of when and how procedures will be conducted (e.g. in person, online, phone, paper, etc.)

All procedures will be conducted in person at the Islamic Centers, except for follow-up phone calls.

Recruitment will occur during regular Friday prayers and religious holidays.

Participants will receive a brochure explaining the study and be screened for eligibility by the Research Assistant (RA). Eligible participants will be given a telephone contact for enrollment at a more convenient time.

The consent process will involve verbal explanation, providing the consent form in English, and allowing participants to ask questions. Follow-up surveys and confirmations will be conducted via phone calls.

4. A description of all research measures/tests/interventions that will be used, including analyses/tests conducted on specimens/biological samples (if applicable)

**Power Analysis:** No power analysis for this study. A target sample size of 20 participants has been determined based on PhD committee, the purpose of the project is training for the STUDENT.

Measures: Validated scales and surveys will be used to measure

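### The sample-size justification is wrong as written: its inputs give 165 rather than 10, it assumes a control group the trial lacks, and it contradicts the stated target of 20 with no power analysis

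*Combined protocol and SAP*

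**What the plan says.** Study Population, question 3, asks how the number of participants was reached and why it is adequate. The answer assumes a 10% rise in screening and vaccine uptake. It bases a power analysis on a t-test, "assuming the use of the student T-test to assess the difference in outcome between the intervention and control groups". It then says the size came from a calculator for an unlimited population, "using a confidence interval of 80%, a standard deviation of 0.5, and a margin of error of 5" percent. It ends: "The study requires 10 participants for intervention to test the feasibility of the program". The same answer separately gives 10 women for the focus-group work, so this second 10 is not the focus group.

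Other current sections say something different:

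- Study Procedures, question 6, item 1 (Study Design): "Part 2 is a single-arm pre and post-test trial".
- Study Procedures, question 6, item 4 (Power Analysis): "No power analysis for this study. A target sample size of 20 participants has been determined based on PhD committee".
- Aim 3, given under both Background, Rationale and Goals and Study Procedures: "We will recruit 20 participants with the same eligibility criteria as in Aim 1", in a single-arm pilot.
- Study Procedures, question 4, summary of the intervention: "The intervention group will consist of 20 participants". The same summary adds: "All participants from both groups will be given the survey at month 0 (baseline").

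The closing summary of the background, just before the Community-Engaged Research Framework, also refers to a two-arm design.

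**The concern.** The answer joins three things that do not belong together: a power analysis for a two-group test, the inputs of a margin-of-error calculation, and a count of 10 that follows from neither. It gives no alpha, sidedness, power, baseline rate or dropout allowance.

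Two consequences follow. First, hypothesis H2 judges feasibility partly by whether enrolment targets are met. With 10 in one place and 20 in others, enrolling 10 to 19 women meets one target and misses the other, so the result could be called either way afterwards. Second, H1 expects significant improvement and the Outcomes text in Study Procedures names screening as the primary outcome. A reader who takes the justification at face value would expect a margin of 5 points and a planned controlled comparison, and could read a null result on uptake as evidence of no effect. The trial offers neither the margin nor the comparison.

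**Working it through.** **1. The plan's own figure.** Inputs from Study Population, question 3: 80% confidence (two-sided z = 1.2816), SD 0.5, margin E = 0.05, unlimited population (no finite-population correction).

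n = (z × SD / E)² = (1.2816 × 0.5 / 0.05)² = 164.2, rounded up to **165**. The plan states 10.

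**2. Other readings of the inputs.**

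| Reading | n |
|---|---|
| 80% one-sided, E = 0.05 | 71 |
| 90% two-sided, E = 0.05 | 271 |
| 95% two-sided, E = 0.05 | 385 |
| 80% two-sided, 5% as total width | 657 |
| 80% two-sided, E = 0.10 | 42 |
| 80% one-sided, E = 0.10 | 18 |
| Two-sample means, difference 0.10, SD 0.5, 80% power, two-sided 5% | 393 per arm |
| Same, one-sided 20% | 142 per arm |
| Paired or one-sample, SD of change 0.5, 80% power, two-sided 5% (normal approximation) | 197 |
| Same, one-sided 20% | 71 |
| Two proportions, +10 points, baseline 10% to 80%, 80% power, two-sided 5%, no continuity correction | 199 to 388 per arm |

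No reading that keeps the inputs as labelled gives 10 or 20. The nearest approach to 10 treats 0.5 as a standardised effect in a paired test at one-sided alpha 0.20 with 80% power, which gives 12. That turns the SD into an effect size and discards the 10% rise, the two-group test and the 5% margin.

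**3. The margin the stated SD delivers.** 80% margin = 1.2816 × 0.5 / √n.

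- n = 10: 0.203, or ±20.3 points.
- n = 20: 0.143, or ±14.3 points.

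**4. Power of the comparison a single arm allows.** Paired t-test (noncentral t), two-sided 5%, mean change 0.10. Two assumptions are needed because the plan settles neither: that the 10% is absolute, and the SD of the change, taken as 0.5 with a range of 0.3 to 0.7.

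| SD of change | n = 10 | n = 20 |
|---|---|---|
| 0.3 | 15.7% | 29.4% |
| 0.5 | 8.8% | 13.6% |
| 0.7 | 6.9% | 9.3% |

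**5. What 20 can show.**

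- Smallest mean change detectable with 80% power at two-sided 5% (paired t): 0.660 SD of the change score with 20 complete pairs, 0.724 SD with 17.
- Retention must exceed 80% under H3. 16/20 is exactly 80% and does not exceed it, so 17/20 is the smallest count that passes. Its exact (Clopper-Pearson) 95% interval is 0.621 to 0.968.

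**The case against.** The strongest reply is that the sentence with the inputs states no sample size, and the next sentence gives 10 as a feasibility number, so there may be no failed calculation. That reading is possible. It leaves a calculation that supports no stated number, for a comparison the trial cannot make, and 10 still conflicts with 20.

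Other points deserve weight:

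- A pilot needs no power calculation, and Study Procedures already says none was done. Agreed. The fault is that the formal justification says otherwise.
- The justification names no power level, since its 80% is labelled as confidence. True. It does say that a power analysis for a controlled comparison underlies the number.
- The phrases about two arms and both groups may refer to the two study parts, because the form has separate consents for a focus group and an intervention group. They do not prove a leftover control arm. They are still unclear and have no place in a single-arm plan.
- For items asking whether a woman has ever been screened or vaccinated, answers should only move from no to yes. A rise of 0.10 then has a change SD of √(0.1 × 0.9) = 0.30, and power is about 16% at n=10 and 29% at n=20. This is the favourable end of the range above, and power is still low.
- The power figures concern uptake, whereas H1 concerns knowledge and acceptance. That is so. Uptake is used because it is the effect the justification itself names.
- The copy reviewed does not show the numbers entered for questions 1 and 2 on the Study Population page. Whatever they are, they cannot make the question 3 text coherent.

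**Conclusion.** The point holds and must be fixed. The mismatch between the inputs and the stated 10, the control group in a single-arm trial, and the conflict with a target of 20 and no power analysis are all plain from the text and need no outside assumption. The claimed precision is too favourable by a factor of about 2.9 at n=20 (14.3 / 5) and about 4.1 at n=10 (20.3 / 5). The statement that uptake is underpowered rests on the assumed absolute rise of 0.10 and the assumed SD of change, but power does not reach 30% at n=20 anywhere in the range examined. Nothing here argues against a pilot of 20. The defect is in its written justification.

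**What to change.** In Study Population, question 3, delete the power-analysis and margin-of-error text and the figure of 10 for the intervention. Replace them with one statement consistent with Study Procedures, for example: *Single arm, n = 20, chosen for feasibility and training; not powered for uptake.* The training purpose is already in Study Procedures, and the feasibility purpose in Aim 3; the statement that uptake is not powered is new and should be made openly.

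Then say what 20 delivers: retention of 17/20 has an exact 95% interval of 62% to 97%, and a paired t-test (two-sided 5%, 80% power) detects a mean change of 0.66 SD of the change score with 20 complete pairs or 0.72 SD with 17. Name the endpoint these figures refer to. This needs care because the plan names awareness as primary in its aims and screening as primary under Outcomes.

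Remove the two-arm wording from the background summary and the reference to both groups from the intervention summary. With the 10 gone, the enrolment target for H2 is the 20 in Aim 3.

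The cost is wording in three places. The stated precision becomes less favourable. No more participants are needed and no procedure changes.
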